### 9.3. Level of Significance

There will not be any statistical comparison between the 2 groups. Within each group, 2-sided 95% CIs will be reported for all analyses when appropriate.

## **9.4. Statistical Analyses**

### **9.4.1. Efficacy Analyses**

#### **9.4.1.1. Primary Efficacy Analyses**

Objective response rate is defined as the percentage of subjects with a CR/CMR or PR/PMR as determined by revised response criteria for DLBCL ([Cheson et al 2014](#)).

The ORR as determined by the IRC and its 95% exact binomial CIs will be calculated for subjects in Group A. This is considered the primary efficacy analysis of the study.

The ORR as reported by the investigator and its 95% exact binomial CIs will also be calculated for subjects in Group A.

Response data will be analyzed when all subjects have received at least 1 postbaseline disease assessment, or have progressed, withdrawn from the study, or died.

#### **9.4.1.2. Secondary Efficacy Analyses**

Duration of response is defined as the time from first documented evidence of CR/CMR or PR/PMR until disease progression or death due to any cause among subjects who achieve an overall response (ie, CR/CMR or PR/PMR) as determined by revised response criteria for lymphomas ([Cheson et al 2014](#)). For subjects who have not progressed and are still alive at the time of the analysis, DOR will be censored on the day of last evaluable disease assessment. For subjects who have discontinued study or have started other anticancer treatment, DOR will be censored on the day of last evaluable disease assessment documenting absence of PD/PMD before the discontinuation or the start of the new anticancer treatment.

Progression-free survival is defined as the time from the date of first dose of the study drug to the first documented disease progression as determined by revised response criteria for lymphomas ([Cheson et al 2014](#)), or death due to any cause, whichever occurs first. For subjects who have not progressed and are still alive at the time of the analysis, PFS will be censored on the day of last evaluable disease assessment. For subjects who have discontinued study or have started other anticancer treatment, PFS will be censored on the day of last evaluable disease assessment documenting absence of PD/PMD before the discontinuation or the start of the new anticancer treatment. For subjects who have no baseline or no postbaseline disease assessment, PFS will be censored with censored duration of 1 day.

The Kaplan-Meier estimation of median DOR and PFS as determined by the IRC and its 95% CIs will be provided for subjects in Group A.

The Kaplan-Meier estimation of median DOR and PFS as reported by the investigator and its 95% CIs will also be provided for subjects in Group A.

Overall survival is defined as the time from the date of first dose of study drug to death due to any cause. For subjects who are still alive at the time of the analysis, OS will be censored on the date the subjects is last known to be alive. The Kaplan-Meier estimation of median OS and its 95% CIs will be provided for subjects in Group A.

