7.2.2. Best Overall Response and Overall Response Rate

For responses by IRC, the best overall response for each subject will be provided by the oncologist.

For investigator-reported responses, the best overall response is the best response recorded before and including the first PD, in the order of CR/CMR, PR/PMR, SD/NMR, PD/PMD, and NE. In the case of SD/NMR, assessment must meet the SD/NMR criteria at least once on or after Day 49. Subjects who fail to meet this criterion will have best response of PD/PMD if the next available assessment after the initial assessment indicates PD/PMD or will have best response of NE if there are no additional assessments available.

A subject is considered a responder if they have a best overall response of CR/CMR or PR/PMR.

The ORR is the proportion of responders. Subjects who do not have sufficient baseline or on-study response assessment information to be adequately assessed for response status will be included in the denominators in the calculation of ORR.

Best overall response as determined by the IRC will be summarized descriptively for subjects in Group A. The ORR as determined by the IRC and its 95% exact binomial CIs will be calculated for subjects in Group A. Confidence intervals will be calculated based on the exact method for binomial distributions. This is considered the primary efficacy analysis of the study.

Best overall response as reported by the investigator will also be summarized descriptively for subjects in Group A. The ORR as reported by the investigator and its 95% exact binomial CIs will be calculated for subjects in Group A. Confidence intervals will be calculated based on the exact method for binomial distributions.

Response data as determined by IRC and those as reported by the investigator will be analyzed when all subjects have received at least 1 postbaseline disease assessment, or have progressed, withdrawn from the study, or died.

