7.3.2. Progression-Free Survival

Progression-free survival is defined as the time from the date of first dose of the study drug to the first documented disease progression as determined by revised response criteria for lymphomas (Cheson et al 2014), or death due to any cause, whichever occurs first. For responses assessed by the IRC, date of disease progression will be provided by the oncologist. For investigator-reported data, the date of PD will be the timepoint at which progression is first recorded. Censoring for PFS will follow the algorithm outlined in Table 1, which is based on the FDA Guidance for Industry: Clinical Trial Endpoints for the Approval of Cancer Drugs and Biologics (FDA 2007).

Table 1: Evaluation and Censoring of Progression-Free Survival

Situation	Outcome	Date of Progression or Censoring
No baseline tumor assessments	Censored	Day 1
No valid postbaseline response assessments	Censored	Day 1
Progression documented between scheduled response assessments	Progressed	Date of first overall response of PD
No progression	Censored	Date of last valid radiologic assessment (not NE and not missing)
Study discontinuation for undocumented progression	Censored	Date of last valid radiologic assessment (not NE and not missing)
Study discontinuation for toxicity or other reason	Censored	Date of last valid radiologic assessment (not NE and not missing)
New anticancer treatment started	Censored	Date of last valid radiologic assessment (not NE and not missing) on/before starting a new anticancer treatment
Death before first progressive response assessment	Progressed	Date of death
Death between adequate response assessments	Progressed	Date of death
Death or progression after 2 or more missed assessments	Censored	Date of last valid radiologic assessment (not NE and not missing)

NE = not evaluable; PD = progressive disease.

The number of subjects whose disease progressed as determined by the IRC or who died and the number of subjects censored will be summarized for subjects in Group A. The Kaplan-Meier estimation of median PFS as determined by the IRC and its 95% CIs will be provided for subjects in Group A.

The number of subjects whose disease progressed as reported by the investigator or who died and the number of subjects censored will also be summarized for subjects in Group A. The Kaplan-Meier estimation of median PFS as reported by the investigator and its 95% CIs will be provided for subjects in Group A.

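### Protocol 9.4.1.2, read literally, censors PFS at 1 day for a subject who dies before any postbaseline scan, and SAP Table 1 has an event row and a censoring row for that subject with no order between them

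*Protocol*

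**What the plan says.** **Protocol 9.4.1.2.** PFS runs from first dose to documented progression or death from any cause. Protocol 2.2.2 defines the endpoint the same way. Two censoring sentences in that paragraph matter here:

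- The first is restricted to survivors: "For subjects who have not progressed and are still alive at the time of the analysis, PFS will be censored" at the last evaluable assessment.
- The last has no such restriction: "For subjects who have no baseline or no postbaseline disease assessment, PFS will be censored with censored duration of 1 day".

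**SAP 7.3.2.** The definition again counts progression "or death due to any cause, whichever occurs first". Censoring then follows Table 1, where these rows bear on the point:

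| Row | Outcome | Date |
|---|---|---|
| Missing baseline tumor assessment | Censored | Day 1 |
| "No valid postbaseline response assessments" | Censored | Day 1 |
| "Death before first progressive response assessment" | Progressed | Date of death |
| "New anticancer treatment started" | Censored | Last valid scan on or before the new treatment |
| Study discontinuation (two rows) | Censored | Last valid scan |
| "Death or progression after 2 or more missed assessments" | Censored | Last valid scan |

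No footnote, row order or text ranks one row above another. SAP 4.1.4 deals only with partial death dates. SAP 10.1 declares no change to Protocol-defined analyses.

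**The concern.** Take a subject who is dosed on Day 1 and dies in Week 5, before the first scheduled scan at Week 9. The PFS definition makes this an event. The last Protocol censoring sentence makes it a 1-day censored record. Table 1 supports both answers, so two programmers could each follow the written text and produce different PFS curves, by IRC and by investigator.

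The plan expects such subjects. The full analysis set needs only one dose, and both the response analysis and the interim look name death as an alternative to having been evaluated.

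If the Day 1 rule were followed, these deaths would leave the risk set before any event is counted. The remaining curve would describe only subjects who lived long enough to be scanned, and it would be too high.

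**Working it through.** **1. No planned figure to reproduce.** Neither document states a PFS assumption or an expected number of early deaths. The passages can be compared directly, and the size of the difference can only be illustrated.

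**2. The text, case by case, for a subject with no valid postbaseline scan.**

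- Alive, no new treatment: all rules agree on censoring at Day 1.
- Dead, no new treatment, still on study, fewer than two missed assessments: event by the PFS definition and by the Table 1 death row; censored at Day 1 by the last Protocol sentence and by the Table 1 no-postbaseline row. This is the conflict.
- Dead after new treatment, study discontinuation or two missed assessments: another censoring row also applies, and its rank against death is not stated either.

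The missing-baseline version has the same flaw but should be nearly empty, because Protocol 7.5.1 and 7.5.2 require screening imaging.

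**3. Effect on the curve if the Day 1 rule is used.** Let d be the share of subjects who die unscanned and whom no other row censors, among subjects not otherwise censored at Day 1. Let G(t) be the Kaplan-Meier PFS of the rest.

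- Death as event: S(t) = (1−d) × G(t) once the early deaths have occurred.
- Day 1 rule: S(t) = G(t).
- Ratio: 1/(1−d).

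| d (assumed) | 5% | 10% | 15% | 20% |
|---|---|---|---|---|
| 1/(1−d) | 1.05 | 1.11 | 1.18 | 1.25 |

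If some of these subjects stay censored under a retained row, d shrinks. With D the share of all subjects who die unscanned and f the part of D that stays censored, d = D(1−f)/(1−Df). For D = 10% and f = 50%: d = 0.05/0.95 = 5.3%, and the ratio is 1.06. D and f are assumptions.

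**4. Effect on the median, the summary actually planned.** Take N = 100 (Group A), 10 early deaths on Day 35, k progressions on Day 63 and the rest on Day 126. Then S(63) is (90−k)/100 with deaths as events and (90−k)/90 under the Day 1 rule.

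| k | Deaths as events: S(63), median | Day 1 rule: S(63), median |
|---|---|---|
| 35 | 0.55, Day 126 | 0.61, Day 126 |
| 42 | 0.48, Day 63 | 0.53, Day 126 |
| 50 | 0.40, Day 63 | 0.44, Day 63 |

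The median moves only when the curve is near 0.5 at a scan, and then by one scan interval.

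A wider grid used exponential progression with medians of 8, 12, 16 and 20 weeks, d of 5, 10, 15 and 20%, and scans at Weeks 9, 18, 27 and 45. The underlying scan-dated median is the same under both rules in 12 of 16 settings. In the other four it moves by 9 weeks.

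Sample medians differ more often than that grid suggests. In 3,000 simulated trials of 100 subjects (12-week progression median, f = 0), both rules gave the same median in about 92, 75, 55 and 33% of trials at D = 5, 10, 15 and 20%.

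**5. Scale against sampling error.** With a 12-week median and d = 10%, PFS just after the Week 18 scan is 0.5^(18/12) = 0.354 under the Day 1 rule and 0.9 × 0.354 = 0.318 with deaths as events. The gap is about 3.5 points. The 95% half-width is 1.96 × √(0.318 × 0.682/100) = 0.091, or about 9 points. Week 18 PFS is not a planned estimate; it only shows how far apart the planned curves would lie.

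**6. What is not touched.** ORR: subjects who cannot be assessed "will be included in the denominators in the calculation of ORR". DOR exists only for responders, who have a scan. OS counts every death. The futility rule uses responses only.

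**The case against.** The strongest reply is that the SAP already answers the question. Both documents define PFS with death as an event, censoring ordinarily concerns subjects without an event, and Table 1 has a specific row for early death. A careful statistician would follow that row. This largely stands: it is why the point is a contradiction in wording and not a finding of bias. It does not remove the point. The Protocol sentence omits the restriction to survivors that its neighbor carries, and the SAP declares no departure from the Protocol. Someone checking the SAP against the Protocol would find explicit support for censoring.

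A second reply is that every input to the size is assumed and applies only under the less natural reading. That is correct, and the figures should be read as conditional.

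A third is that simply ranking death above everything would silently alter the rules for study discontinuation, new treatment and missed assessments. That is also correct, and the fix has to leave those rows alone unless their rank is stated openly.

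A reader might infer that the trial's PFS will be overstated, or that the primary endpoint or the futility decision is compromised. The documents support neither inference: the first depends on choosing the less natural row, and the second fails on the ORR denominator rule and the response-only futility rule.

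**Conclusion.** Wrong as written; minor. The Protocol's Day 1 sentence contradicts its own PFS definition for subjects who die unscanned, and SAP Table 1 does not say which of its two applicable rows prevails. Confidence is high on the text and low on any effect in practice.

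If the death row is used, there is no bias. If the Day 1 rule is used, later Kaplan-Meier PFS is too high by about 1/(1−d). The median is then either unchanged or, in the settings examined, later by one scan interval. The size rests on assumed values of d and of the progression median. The consequence is confined to secondary PFS by IRC and by investigator, in a single-arm study with no efficacy hypothesis (SAP 7.1) and no historical comparison (Protocol 4.2).

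**What to change.** In SAP Table 1, for example as a footnote, limit the two Day 1 rows (missing baseline assessment, and no valid postbaseline assessment) to subjects with no recorded death. A death before any valid postbaseline assessment is then a PFS event on the date of death. Make the matching change to the last PFS censoring sentence in Protocol 9.4.1.2 at the next amendment.

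In the same place, say that the existing censoring rows for new anticancer treatment, study discontinuation and two or more missed assessments are unchanged by this edit, and state how each ranks against the death rows. Those rankings are separate choices and should be made explicitly.

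Cost: no new data. The SAP footnote is enough to settle programming. The Protocol wording needs the usual sponsor and IRB/IEC approval, so it can wait for an amendment made for other reasons. The downside is that reported PFS may be slightly less favorable than under the literal Day 1 rule.

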## **9.4.2. Safety Analyses**

### **9.4.2.1. Adverse Events**

A treatment-emergent adverse event (TEAE) is any AE either reported for the first time or worsening of a pre-existing event after first dose of study drug. Analysis of AEs will be limited to TEAEs, but data listings will include all AEs regardless of their timing to study drug administration. Adverse events will be tabulated by the MedDRA preferred term and system organ class. Severity of AEs will be based on the NCI CTCAE v4.03 using Grades 1 through 4.

The subset of AEs considered by the investigator to have a relationship to study drug will be considered to be treatment-related AEs. If the investigator does not specify the relationship of the AE to study drug, then the AE will be considered treatment-related. The incidence of AEs and treatment-related AEs will be tabulated.

An overall summary of AEs will include number (%) of subjects reporting any TEAEs, any SAEs, any Grade 3 or 4 TEAEs, any treatment-related TEAEs, any fatal TEAE, and any TEAEs leading to treatment interruption/dose reduction/discontinuation.

Number (%) of subjects reporting any TEAEs, any SAEs, any Grade 3 or 4 TEAEs, any treatment-related TEAEs, any treatment-related SAEs, any treatment-related Grade 3 or 4 TEAEs, any fatal TEAE, and any TEAEs leading to treatment interruption/dose reduction/discontinuation will be tabulated by system organ class and preferred term.

### **9.4.2.2. Clinical Laboratory Tests**

Laboratory data will be classified into Grades 1 through 4 using CTCAE v4.03 when applicable. The following summaries will be produced for the laboratory data:

- Descriptive statistics of the value and change from baseline at each assessment time will be provided.
- For laboratory parameters that have CTC grading, shift tables will be provided showing change in CTC grade from baseline to the worst grade postbaseline.
- For laboratory parameters where CTC grades are not defined, shift tables from baseline to the worst postbaseline value will be produced using the low/normal/high classifications based on laboratory reference ranges.

Categorical laboratory data will be tabulated by visit at baseline and postbaseline visits when necessary.

### **9.4.2.3. Vital Signs**

Descriptive statistics and mean change from baseline will be summarized for vital signs (weight, blood pressure, pulse, respiratory rate, and body temperature) at each assessment time. Vital sign results will be reviewed for clinically notable abnormalities (see [Table 12](#)), and subjects

exhibiting clinically notable vital sign abnormalities will be listed. A value will also be considered an "alert" value if it is outside the established range and shows a > 25% change from baseline. The abnormal values for subjects exhibiting alert vital sign abnormalities will be listed

**Table 12: Criteria for Clinically Notable Vital Sign Abnormalities**

Parameter	High Threshold	Low Threshold
Systolic blood pressure	> 155 mmHg	< 85 mmHg
Diastolic blood pressure	> 100 mmHg	< 40 mmHg
Pulse	> 100 bpm	< 45 bpm
Temperature	> 38°C	< 35°C
Respiratory rate	> 24/min	< 12/min

[figure not shown]
**9.4.2.4. Electrocardiograms**

Descriptive statistics and mean change from baseline will be summarized for the ECG parameter at each assessment time. Average of all values before the first dose of study drug will be used as the baseline value. Criteria for clinically notable ECG abnormalities are defined (see Table 13). The abnormal values for subjects exhibiting clinically notable ECG abnormalities will be listed. Alert ECG values are defined as an absolute value outside the defined range and absolute percentage change > 25% (30% for QRS) interval. The abnormal values for subjects exhibiting alert ECG abnormalities will be listed. Outliers of QT, QTcB, and QTcF, defined as absolute values > 450 milliseconds or change from baseline > 30 milliseconds, will also be listed.

[figure not shown]
**Table 13: Criteria for Clinically Notable Electrocardiogram Abnormalities**

Parameter	High Threshold	Low Threshold
QTcF	> 460 msec	< 295 msec
PR	> 220 msec	< 75 msec
QRS	> 120 msec	< 50 msec
QT	> 500 msec	< 300 msec
RR	> 1330 msec	< 600 msec

QTcF = Fridericia correction.

### **9.5. Analyses for the Independent Data Monitoring Committee**

Preplanned analyses of safety will be provided to the IDMC as specified in the IDMC charter. In addition, the IDMC will make recommendations to the sponsor at the planned interim futility analysis in Group A (see Section 9.6). The process by which the IDMC will make recommendations and decisions will be documented in the IDMC charter.

### **9.6. Interim Analysis**

An interim futility analysis is planned when the first 40 subjects in Group A have been treated and have been evaluated for response or have permanently discontinued study treatment because of disease progression, withdrawal of consent, or death. Group A of the study will be terminated for futility if  $\leq 13$  of the 40 subjects have responded (ie, CR/CMR or PR/PMR) based on assessments provided by the IRC; otherwise the study will continue. The futility boundary is determined using a spending function of HSD(-4). A timely assessment of response will be performed to avoid the risk of overenrollment.

## **10. ETHICAL CONSIDERATIONS AND ADMINISTRATIVE PROCEDURES**

### **10.1. Investigator Responsibilities**

This study will be performed in accordance with ethical principles that originate in the Declaration of Helsinki and conducted in adherence to the study Protocol; GCPs as defined in Title 21 of the US CFR Parts 11, 50, 54, 56, and 312; ICH E6 GCP consolidated guidelines; and local regulatory requirements as applicable to the study locations.

The investigator will be responsible for:

- Permitting study-related monitoring, sponsor audits, IRB/IEC review, and regulatory inspections by providing direct access to source data and other relevant clinical study documents.
  - Monitoring: Qualified representatives of the sponsor or its designee, study monitors, will monitor the study according to a predetermined plan. The investigator must allow the study monitors to review any study materials and subject records at each monitoring visit.
  - Auditing: Qualified representatives of the sponsor or its designee may audit the clinical study site and study data to evaluate compliance with the Protocol, applicable local clinical study regulations, and overall study conduct. The investigator must allow the auditors to review original source records and study documentation for all subjects.
  - Regulatory inspection: Regulatory authorities may conduct an inspection of the study and the site at any time during the development of an investigational product. The investigator and staff are expected to cooperate with the inspectors and allow access to all source documents supporting the eCRFs and other study-related documents. The investigator must immediately notify the sponsor when contacted by any regulatory authority for the purposes of conducting an inspection.
- Obtaining informed consent and ensuring that the study subjects' questions have been answered and the subjects fully understand study procedures:
  - Informed consent must be obtained before any study-related procedures are conducted, unless otherwise specified by the Protocol.
  - Informed consent must be obtained using the IRB/IEC-approved version in a language that is native and understandable to the subject. A template will be provided by the sponsor or its designee. The sponsor or its designee must review and acknowledge the site-specific changes to the ICF template. The ICF must include a statement that the sponsor or its designee and regulatory authorities have direct access to subject records.

- Obtaining approval from the IRB/IEC before the start of the study and for any changes to the clinical study Protocol, important Protocol deviations, routine updates, and safety information in accordance with institutional requirements and local law.
  - The investigator is responsible for ensuring that the safety reports provided by the sponsor are reviewed and processed in accordance with regulatory requirements and with the policies and procedures established by the IRB/IEC.
- Adhering to the Protocol as described in this document and agreeing that changes to the Protocol procedures, with the exception of medical emergencies, must be discussed and approved, first, by the sponsor or its designee and, second, by the IRB/IEC. Each investigator is responsible for enrolling subjects who have met the specified eligibility criteria.
- Retaining records in accordance with all local, national, and regulatory laws, but for a minimum period of at least 2 years after the last marketing application approval in an ICH region and until there are no pending or contemplated marketing applications in an ICH region, or if not approved, 2 years after the termination of the test article for investigation to ensure the availability of study documentation should it become necessary for the sponsor or a regulatory authority to review.
  - The investigator must not destroy any records associated with the study without receiving approval from the sponsor. The investigator must notify the sponsor or its designee in the event of accidental loss or destruction of any study records. If the investigator leaves the institution where the study was conducted, the sponsor or its designee must be contacted to arrange alternative record storage options.
  - All eCRF data entered by the site (including audit trail), as well as computer hardware and software (for accessing the data), will be maintained or made available at the site in compliance with applicable record retention regulations. The sponsor will retain the original eCRF data and audit trail.

